1.1.3.3. Pharmacology

SLN360 PD was evaluated by measuring serum Lp(a) concentration and the effects of SLN360 on concentrations of other lipids and lipoproteins. The lipid profile included high-density lipoprotein cholesterol, low-density lipoprotein cholesterol (LDL-C), total cholesterol, triglycerides and apoB.

The maximal total and percent changes in Lp(a) following administration of placebo or SLN360 across the four dose groups (30 mg, 100 mg, 300 mg and 600 mg) are presented in [Table 2](#). Reductions in Lp(a) were dose proportional and reached a maximal median (interquartile range) percent change of -98% (-98%, -97%) following administration of 600 mg SLN360. The greatest percent change in Lp(a) level concentration was achieved between 30 days and 60 days after dosing for all treatment groups. Subsequently, concentrations gradually rose, but they had not returned to baseline values 150 days post-dose for the 100 mg, 300 mg and 600 mg treatment groups. Median Lp(a)

[figure not shown]

Study Number: SLN360-002	Compound No.: SLN360
Protocol	Version: 1.0

Study Number: SLN360-002	Compound No.: SLN360
Protocol	Version: 1.0

Figure 1 Percent change in lipoprotein(a) concentration from baseline to Day 150 post-dose

Lp(a)=lipoprotein A

Note: ranges presented depict minimum and maximum values.

SLN360 produced a moderate, dose-dependent reduction in apoB-containing lipoproteins (i.e., Lp[a] and LDL, and reflected by total cholesterol). Mean levels were reduced by a maximum of 18% for total cholesterol and 26% for LDL-C, both following administration of the 600 mg dose. Smaller reductions were observed at lower doses. The maximum reduction in the mean level of apoB was 24% at 30 days after the 600 mg dose and 19% at 14 days after the 300 mg dose. The maximal mean percent reduction of oxidised LDL was 20% in the 600 mg dose group at Day 30 and 11% in the 300 mg dose group at Day 90. There was no evidence of an SLN360-mediated effect on triglycerides or high-density lipoprotein cholesterol.

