12.4. Data Analysis Considerations

Analysis of variance methodology will be used to test for differences between active treatment and placebo for the primary endpoint of time-averaged change from baseline in Lp(a) and secondary endpoints including time-averaged, percent and absolute change

Study Number: SLN360-002	Compound No.: SLN360
Protocol	Version: 1.0

from baseline in Lp(a) and other lipids/lipoproteins including LDL-C, total cholesterol and apoB. Multiplicity adjustment to the type 1 error will be applied for comparisons of active treatment arms versus placebo with similar dosing regimens and will be described in the SAP. Pairwise comparisons between active arms will be considered exploratory and multiplicity adjustments will not be applied.

The distribution of Lp(a) is expected to be positively skewed, but the percentage change from baseline Lp(a) value is not expected to have the same distribution; therefore, parametric testing is appropriate. Testing the assumption of normality will be performed before any formal analysis and sensitivity analyses will be undertaken, if required. Full details of this process will be included in the SAP.

Baseline will be defined as last non-missing observation/measurement before the start of study drug administration.

Descriptive statistics will be used to summarise safety and PD endpoints by treatment group.

Each SLN360 dosing regimen will be presented separately.

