2.2.4 Sample Size Determination

A total of five treatment groups and approximately 160 participants are planned. Each placebo group will include 20 randomly allocated participants, and each SLN360 group will include 40 randomly allocated participants. This will result in a total of 120 participants exposed to SLN360 and 40 participants exposed to placebo. The placebo groups will be analysed and reported both separately and in combination.

The treatment effect observed in the first-in-human (FIH) Phase 1 study (APOLLO; ClinicalTrials.gov identifier NCT04606602; EudraCT identifier 2020-002471-35) between placebo and 300 mg SLN360 at Day 150 (the smallest effect observed at the lowest dose to be used in the proposed study) was approximately 60% with a conservative pooled standard deviation of 40%. As few as 10 participants per arm would give approximately 90% power to detect this magnitude of difference, at the 5% significance level ($p <0.05$).

The proposed sample size, even separating the placebo arms with a different dose frequency, is expected to be more than adequate to demonstrate the SLN360 effect on Lp(a). The larger sample size should allow a more robust evaluation of safety at these doses and dose frequencies than a smaller sample size that may be expected in a Phase 2 study.

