3.4.1 Primary Endpoint

Primary Estimand

The primary estimand for this study is defined by the following attributes:

- Target population: participants with elevated Lp(a) at high risk of ASCVD events
- Treatments: SLN360 versus placebo
- Primary outcome measure: time-averaged percent change in Lp(a) molar concentration from Day 1 pre-dose to Week 36
- Analysis population: Pharmacodynamic Population
- Intercurrent events: prohibited medications/procedures and permitted medications (defined in protocol section 9.2 and 9.3), death, early withdrawal from study drug, and early withdrawal from the study.
- Analysis set and handling of intercurrent events: Treatment policy strategy will be used. All values of Lp(a) from scheduled assessments up to Week 36 will be included in the calculation of time-averaged percent change for each participant
- Population level summary: difference in mean time-averaged percent change in Lp(a) from Day 1 pre-dose to Week 36 between treatment groups

Time-averaged percent change from Week 4 to Week 36 is calculated from Week 4 corrected area under the curve (AUC) using linear trapezoidal method from Week 4 to Week 36 divided by the per-patient total time interval. Note that the Day 1 pre -dose values will be excluded from the time-averaged calculations (i.e., for each participant, the initial value included in the calculation will be from their first scheduled post-baseline assessment). Furthermore, the actual analysis day of each assessment will be used in the AUC calculation.

If the last available measurement of Lp(a) is before Week 36, time-averaged percent change in Lp(a) from Day 1 pre-dose to Week 36 will be calculated by arithmetic mean of all percent changes in Lp(a) from Day 1 pre-dose up to the last available time point before Week 36.

Analysis of variance will be used to test for differences between each active treatment group (i.e., Group 3, 4, or 5 in Table 1) and the pooled placebo groups (i.e., Groups 1 and 2 in Table 1 combined) for time-averaged percent change in Lp(a). Time-averaged percent change from Day 1 pre-dose to Week 36 in Lp(a) will be the dependent variable and treatment will be included as a factor. The least squares means, standard errors, and 2-sided 95% confidence intervals for each treatment group and for the pairwise comparisons between the SLN360 and placebo groups will be provided.

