Holm's procedure will be used to control multiplicity of pairwise comparisons between each SLN360 group and the pooled placebo group. p-values will be first ordered from the smallest to the largest. $p_{(1)}$ represents the smallest value, $p_{(2)}$ the next-smallest p-value, $p_{(3)}$ the third-smallest p-value.

- (1) The test begins by comparing the smallest p-value, $p_{(1)}$, to 0.05/3 or 0.0167. If this $p_{(1)}$ is less than 0.0167, the pairwise treatment comparison with this p-value is considered significant.
- (2) The test then compares the next-smallest p-value, $p_{(2)}$, to 0.05/2 or 0.025. If this $p_{(2)}$ is less than 0.025, the pairwise treatment comparison with this p-value is also considered significant.
- (3) The test then compares the next ordered p-value, $p_{(3)}$, to 0.05. If this $p_{(3)}$ is less than 0.05, the pairwise treatment comparison with this p-value is also considered significant.

Pairwise comparisons between SLN360 groups will be provided and considered exploratory and multiplicity adjustments will not be applied.

P-values below 0.05 will still be considered nominally significant.

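### The primary ANOVA uses one residual variance for pooled placebo and three active arms that are unlikely to spread equally; group-specific variances are a cheap improvement

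*SAP*

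**What the plan says.** SAP 3.4.1 states: "Analysis of variance will be used to test for differences between each active treatment group" (Groups 3, 4 and 5) and the two placebo groups combined. Time-averaged percent change "in Lp(a) will be the dependent variable and treatment will be included as a factor". No other term is named, and no Welch, group-specific or robust variance. The output is "The least squares means, standard errors, and 2-sided 95% confidence intervals for each treatment group" and for each SLN360-placebo difference. For the regimens, "Pairwise comparisons between SLN360 groups will be provided and considered exploratory and multiplicity adjustments will not be applied"; the model is not stated, and I take it to be the same ANOVA. SAP 3.4.2 carries these conventions to the time-averaged secondary endpoints.

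Protocol 12.4 argues that percent change will not share the skew of Lp(a) itself, so parametric testing is suitable. It adds: "Testing the assumption of normality will be performed before any formal analysis and sensitivity analyses will be undertaken, if required", and leaves the full details to the SAP. The SAP contains no normality check, trigger or fallback, and its section 6 declares no changes from the protocol. Neither document mentions unequal variances. The only SD given for Lp(a) change is the one used for sample size in SAP 2.2.4: "a conservative pooled standard deviation of 40" percent.

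**The concern.** A one-way ANOVA averages the arm variances and applies the result to every pairwise difference. That is harmless if the arms spread alike, but here there is reason to expect otherwise. Percent change is bounded at -100%, and protocol 8.2 anticipates reductions of 80 to 90%, so active participants may be compressed towards the bound while placebo participants are not. The active arms may also differ from one another: Table 7 predicts that 94.0% (300 mg Q4M), 68.7% (300 mg Q6M) and 86.7% (450 mg Q6M) of simulated participants exceed an 80% reduction.

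At stake is the accuracy of the reported intervals. The protocol's stated aim is to characterise the regimen with the greatest magnitude and duration of reduction at the lowest dosing frequency. The regimen contrasts serve that aim, and under a pooled error term their precision depends partly on placebo scatter.

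**Working it through.** **1. The plan's own power figure.** Inputs from SAP 2.2.4: difference 60, SD 40, 10 per arm, 5% level. SE = 40 × √(2/10) = 17.89; 60/17.89 = 3.354; 3.354 − 1.960 = 1.394; power = Φ(1.394) = 91.8%. With the noncentral t on 18 df it is 88.7%. Both agree with the stated figure of about 90%, so planning used a two-sided test and one common SD.

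**2. Formulas.** Pooling placebo gives four groups of 40.
- MSE = mean of the four arm variances, on 160 − 4 = 156 df (t = 1.975).
- ANOVA SE of any difference = √(2 × MSE/40).
- True SE = √((s_i² + s_j²)/40).
- Coverage ≈ 2Φ(1.975 × ANOVA SE / true SE) − 1.

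**3. Placebo more variable.** Assumed, not from the documents: SD 8 in every active arm, placebo SD 15, 20 or 25.

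| Placebo SD | MSE | ANOVA SE | True SE v placebo | Coverage v placebo | ANOVA half-width between regimens |
|---|---|---|---|---|---|
| 15 | (225 + 192)/4 = 104.25 | 2.28 | √(289/40) = 2.69 | 90.7% | 4.5 |
| 20 | (400 + 192)/4 = 148 | 2.72 | √(464/40) = 3.41 | 88.5% | 5.4 |
| 25 | (625 + 192)/4 = 204.25 | 3.20 | √(689/40) = 4.15 | 87.2% | 6.3 |

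The true between-regimen SE is √(128/40) = 1.79 in each row, so a separate-variance half-width is about 3.6. The pooled intervals are 27% to 77% too wide. The placebo group's own interval, also to be reported, would cover 82%, 77% and 74%.

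**4. Equal spread, and placebo less variable.** With SD 10 in all arms, the ANOVA and Welch half-widths are 4.4 and 4.5, and coverage is 95%: no effect. With placebo SD 10 and active SDs 20, MSE = (100 + 1200)/4 = 325 and the ANOVA half-width is 8.0. Against placebo Welch gives 7.1, so the ANOVA interval is too wide (coverage about 97.5%). Between regimens Welch gives 8.9, so it is too narrow (about 92.5%).

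**5. Active arms that differ.** Taking a lognormal residual ratio and assumed median reductions of 90%, 85% and 88%, Table 7 gives SDs of about 5 (300 mg Q16W), 12 (300 mg Q24W) and 6 (450 mg Q24W). With placebo SD 10 the errors then run both ways:
- 300 mg Q24W v placebo: ANOVA 3.8, Welch 4.8; coverage 89%.
- 300 mg Q16W v placebo: 3.8 against 3.6; 97%.
- 300 mg Q24W v 450 mg Q24W: 3.8 against 4.2; 93%.
- 300 mg Q16W v 450 mg Q24W: 3.8 against 2.6; above 99%.

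With these SDs, every interval against placebo is too narrow and every regimen interval too wide only if placebo SD exceeds about 12. The SDs themselves are weakly determined: for 300 mg Q24W they run from 4 (median 82%) to 29 (median 88%).

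**6. Separate variances.** In simulated normal data, Welch coverage was about 95% in every case tried, whichever arm varied more.

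**7. Significance against placebo.** With SD 40 in every arm and 40 v 40, z = 60/(40 × √(2/40)) = 6.7, and power exceeds 99.9% at the first Holm threshold of 0.0167.

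**The case against.** The documents do not show that placebo varies more, and several features point the other way. The protocol calls Lp(a) genetically determined and says diet and physical activity do not influence it. Background lipid therapy must be stable, and the endpoint averages up to nine visits (Weeks 4 to 36). All of this favours a small placebo SD. The active arms keep participants who stop study drug, under a treatment-policy strategy. If 3 of 40 averaged -40% rather than -87%, an SD of 8 would become √(64 + 0.075 × 0.925 × 47²) = 14.7.

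The tightest Phase 1 spread, a median of minus "98% (-98%, -97%) following administration of 600 mg SLN360", is maximal change after a single dose in six people, at a dose this trial does not use. It illustrates compression but gives no SD for these arms. At 300 mg the Day 150 effect was about 60%, so 300 mg Q24W may not sit near the bound. Table 7 gives tail percentages only, without means or SDs.

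The regimen contrasts are labelled exploratory. Group SDs, quartiles and mean ± SD plots will be reported, so unequal spread would be visible.

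All of this stands. It removes any claim about direction, but it does not support equal variances: a rebound or dropout effect in some active arms is itself a source of unequal spread. Seeing the inequality in a summary table does not correct the intervals.

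**Conclusion.** A cheap improvement, not an error shown on the page. One residual variance for these four groups is an assumption that the plan neither supports nor checks, and separate variances hold coverage in either direction. The figures of 91% to 87% coverage, and 4.5 to 6.3 points instead of 3.6, depend on the assumed SDs (active 8, placebo 15 to 25), four groups of 40 and normal data.

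A reader might infer that the intervals against placebo are too narrow and those between regimens too wide, so that the SAP is wrong as written. The documents do not support that: no SD by arm appears in the available text, and the errors reverse if placebo varies less. A reader might also infer that the protocol promised a sensitivity analysis for unequal variance. Protocol 12.4 concerns normality, and its sensitivity analyses are conditional. What is missing is the normality check and its details, a secondary documentation gap that sits beside a statement of no changes.

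The conclusion against placebo is not in doubt. The effect is on how accurately the intervals express uncertainty.

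**What to change.** In SAP 3.4.1, and by reference in 3.4.2, fit the model with a separate residual variance per treatment group and Satterthwaite degrees of freedom (in SAS, PROC MIXED with a REPEATED statement and GROUP=treatment), or specify Welch-type pairwise intervals. State that this covers both the placebo contrasts and the between-regimen contrasts. The cost is a sentence in the SAP, one model option and slightly fewer degrees of freedom.

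Secondary: add the normality check with its trigger and fallback, or record its omission and the reason in SAP section 6.

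A log-ratio sensitivity analysis is optional and should also use group-specific variances. It changes the estimand, gives more weight to values substituted at half the quantification limit, and can reverse the inequality. For example, a residual ratio of 0.12 with SD 0.08 has log SD √ln(1 + (0.08/0.12)²) = 0.61, while a placebo ratio of 1.0 with SD 0.20 has log SD √ln(1.04) = 0.20.

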3.4.2 Secondary Pharmacodynamics and Efficacy Endpoints

Time averaged secondary endpoints will be calculated and analyzed using the same conventions as the primary endpoint.

For each PD parameter, percent and absolute change from Day 1 pre-dose to each visit will be summarized descriptively. The least squares means, standard errors, and 2-sided 95% confidence intervals from analysis of variance will be provided for each treatment group and for the pairwise comparisons of each SLN360 group and placebo. Figures displaying mean (+/- standard deviation) by visit will be plotted for Lp(a), Apolipoprotein B, LDL Cholesterol, HDL Cholesterol, Total Cholesterol, Triglycerides, Oxidized Phospholipids, and C Reactive Protein will be displayed at baseline and each post-baseline visit. Additionally, figures for mean change and percent change (+/- standard deviation) from baseline will be presented for Lp(a), Apolipoprotein B, LDL Cholesterol, and C Reactive Protein will be displayed for each post-baseline visit.

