8.2. Dose Rationale

Data from SAD administration in the FIH study and from modelling of nonclinical data (LYO-X Report No.: [LYO-X-2022-06-0003](#)) indicate that the safe, tolerable and effective doses of SLN360 for evaluation in this Phase 2 study are 300 mg and 450 mg. SLN360 and placebo will be administered via subcutaneous injection in multiple doses. Placebo and three SLN360 dosing regimens will be evaluated: 300 mg Q16W, 300 mg Q24W and 450 mg Q24W.

Efficacy is defined as a combination of magnitude of Lp(a) reduction and the duration over which that reduction persists. Data from the FIH study suggest that a reduction of 80 to 90% in Lp(a) levels from baseline sustained for more than 12 weeks is anticipated at these doses.

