2.3.2.2 Pharmacodynamics and Efficacy

The secondary pharmacodynamic (PD) and efficacy endpoints are:

- Time-averaged percent change in Lp(a) molar concentration from baseline to Week 48 and Week 60.
- Time-averaged absolute change in Lp(a) molar concentration from baseline to Week 36, Week 48, and Week 60.
- Time-averaged percent and absolute change in Lp(a) mass concentration, ApoB, LDL-C, HDL-C, total cholesterol and triglycerides, from baseline to Week 36, Week 48, and Week 60.
- Percent and absolute change in Lp(a) molar concentration, Lp(a) mass concentration, ApoB, LDL-C, HDL-C, total cholesterol, triglycerides, oxidized phospholipids, and C-reactive protein, from baseline by visit (i.e., not time-averaged)

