6 CHANGES FROM PROTOCOL-SPECIFIED STATISTICAL ANALYSES

There are no changes from the protocol-specified statistical analyses.

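### Absolute change in Lp(a) is analysed by a treatment-only ANOVA that ignores baseline, which costs precision on a secondary endpoint, and the normality process that Protocol 12.4 assigns to the SAP is missing

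*SAP*

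**What the plan says.** SAP 2.3.2.2 lists as a secondary endpoint: "Time-averaged absolute change in Lp(a) molar concentration from baseline to Week 36, Week 48, and Week 60". SAP 3.4.2 gives its analysis by reference: "Time averaged secondary endpoints will be calculated and analyzed using the same conventions as the primary endpoint". The model referred to is in SAP 3.4.1: "Time-averaged percent change from Day 1 pre-dose to Week 36 in Lp(a) will be the dependent variable and treatment will be included as a factor". Baseline is used to form the change but is not a model term. No unequal-variance or robust method is named.

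For by-visit percent and absolute change, SAP 3.4.2 promises least squares means and intervals from analysis of variance against placebo and lists no model terms.

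Protocol 12.4 gives the reason for parametric testing: "The distribution of Lp(a) is expected to be positively skewed, but the percentage change from baseline Lp(a) value is not expected" to share that distribution. It then commits to a check: "Testing the assumption of normality will be performed before any formal analysis and sensitivity analyses will be undertaken, if required". It adds that the SAP will hold the full details. The SAP contains no normality test, trigger or sensitivity analysis, yet its section 6 says: "There are no changes from the protocol-specified statistical analyses".

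**The concern.** Protocol 8.2 says that "a reduction of 80 to 90% in Lp(a) levels from baseline sustained for more than 12 weeks is anticipated at these doses". On drug, the change in nmol/L is then roughly 0.8 to 0.9 times baseline. It inherits the spread and skew of baseline Lp(a), which has an entry floor of 125 nmol/L and no ceiling. On placebo it inherits neither. Three things follow for absolute change:

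- The protocol's argument for parametric testing does not cover it.
- A single pooled residual variance cannot fit both drug and placebo groups.
- Most of the scatter on drug is baseline variation that has already been measured and could be removed.

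At stake are the precision of a secondary endpoint and the accuracy of its intervals. The missing normality process is a separate gap between the two documents. It also touches the primary endpoint, because any fallback would have to be chosen without a prespecified rule.

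**Working it through.** **1. The plan's own figure.** SAP 2.2.4 says the effect "was approximately 60% with a conservative pooled standard deviation of 40" percent. With 10 per arm, two-sided 5%: power = Φ(60/40 × √(10/2) − 1.96) = Φ(1.39) = 91.8% (88.7% by noncentral t), against a stated 90% or so. With 40 v 40 at the strictest Holm level, 0.0167: Φ(1.5 × √20 − 2.39) = Φ(4.31), above 99.9%. These figures are for percent change. The documents give no SD for absolute change, so everything below rests on assumptions.

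**2. Variance of absolute change, by hand.** Assume baseline mean μ = 245.2 and SD σ = 92.6 nmol/L (lognormal, cut at 125). Assume mean reductions f of 85, 80 and 85% in three active groups with SD s = 8 points. Assume placebo mean 0 with SD 12 points, and response independent of baseline. Then Var = f²σ² + s²(μ² + σ²), with σ² = 8,575 and μ² + σ² = 68,688.

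- Placebo: 0.0144 × 68,688 = 989 (SD 31.5)
- 85% group: 0.7225 × 8,575 + 0.0064 × 68,688 = 6,195 + 440 = 6,635 (SD 81.5)
- 80% group: 0.64 × 8,575 + 440 = 5,928 (SD 77.0)

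The baseline term is 6,195/6,635 = 93% of the variance in the 85% group, and zero on placebo.

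**3. What the planned ANOVA reports (40 per group, placebo pooled).** Mean square = (989 + 6,635 + 5,928 + 6,635)/4 = 5,047. Reported SE for any pair = √(5,047 × 2/40) = 15.9.

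- Active v placebo, true SE: √((989 + 6,635)/40) = 13.8. Ratio 1.15, coverage about 2Φ(1.96 × 1.15) − 1 = 97.6%.
- Active v active, true SE: √((6,635 + 5,928)/40) = 17.7. Ratio 0.90, coverage about 92%.

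Simulation of the same case gave 97.4% and 92.2%.

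**4. Common-slope adjustment.** Average slope = (0 + 0.85 + 0.80 + 0.85)/4 = 0.625. Remaining variances:

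- 85% group: 0.225² × 8,575 + 440 = 874
- 80% group: 0.175² × 8,575 + 440 = 703
- Placebo: 0.625² × 8,575 + 989 = 4,339

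Active v placebo SE = √((874 + 4,339)/40) = 11.4, down 17%. Active v active SE = √((874 + 703)/40) = 6.3, down about 65%.

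**5. Simulation tied to Table 7 of the protocol.** Central assumptions: Lp(a) median 200 nmol/L before the cut, log-SD 0.4, within-person CV 12%. The residual fraction is lognormal (log-SD 0.5), with medians set so that 94.0, 68.7 and 86.7% of Groups 3, 4 and 5 exceed an 80% reduction. Placebo SD is 10%, with no discontinuers.

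| Contrast | SE unadjusted | SE common slope | Reduction | ANOVA coverage | ANCOVA with HC3 coverage |
|---|---|---|---|---|---|
| Group 3 v placebo | 14.7 | 10.7 | 27% | 97% | 94% |
| Group 3 v Group 4 | 18.1 | 5.8 | 68% | 92% | 96% |

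A longer run gave 14.5 to 11.1 (23%) and 18.1 to 5.9 (67%).

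The grid had 180 assumption sets: median 150 to 250, baseline log-SD 0.3 to 0.5, CV 10 to 15%, residual log-SD 0.3 to 0.8 by arm, placebo SD 5 or 20%, and 0 or 10% discontinuers.

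| Across the grid | v placebo | Active v active |
|---|---|---|
| Planned ANOVA coverage | 93.9–98.9% (median 97.0) | 89.8–96.3% (median 92.7) |
| SE reduction, common slope | 10–33% (median 20) | 34–74% (median 58) |
| Common slope, HC3 coverage | 92.7–96.5% | 93.1–97.6% |

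Ordinary ANCOVA standard errors covered only 82.9 to 97.2% against placebo (median 89.2). A 20% smaller SE is worth 1/0.8² = 1.56 times the participants.

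**6. The same central case on percent change.** The planned ANOVA gives Group 3 v Group 4 a difference of about 7.5 points, some 3.2 reported SEs. On the absolute scale the difference is 17 nmol/L against a reported SE of 16.4, a ratio of 1.0.

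**7. The normality process.** Protocol 12.4 promises a check, sensitivity analyses if required, and full details in the SAP. SAP sections 3.1 and 3.4 contain none of these, and SAP section 6 declares no changes. These statements cannot all stand. This step needs no simulation.

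**The case against.** Protocol 12.4 itself specifies analysis of variance and names absolute change among its endpoints. The missing covariate is therefore a design weakness, not a departure from the protocol. That stands.

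A reader might infer that the choice of regimen is compromised. The documents do not support this. Protocol 8.2.1 characterises regimens by time-averaged percent reduction, which is the primary endpoint, and SAP 3.4.1 provides active-to-active comparisons on it. Step 6 shows that these already separate Groups 3 and 4 in the central case, although with wider placebo variability and other residual spreads the ratio can fall to about 1.6. For absolute change, active-to-active comparisons follow only from the same-conventions sentence, and SAP 3.4.1 labels such comparisons exploratory.

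A reader might also infer that the percent-change intervals are wrong in a known direction. Only a pooled SD of 40% is given. Over 162 assumed combinations, pooled-error coverage ran from 83.9 to 100%, and every pair could fall on either side of 95%. No direction can be claimed.

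Finally, the remedy is partly a trade. Against placebo, worst-case coverage is 92.7% with HC3 and 93.9% with the planned ANOVA. A model with separate slopes has worst-case active-to-active coverage of 90.3%, hardly better than the planned 89.8%. This is why the common slope with HC3 is preferred.

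**Conclusion.** The concern holds as a loss of precision and of interval accuracy on a secondary endpoint. Around the central assumptions, the planned interval for absolute change is conservative against placebo (about 96 to 97%) and somewhat too narrow between active groups (about 92 to 93%). Common-slope adjustment would cut the SE by about 20 to 30% and by more than half, respectively; the grid in step 5 shows how far both can vary. That absolute change on drug depends on baseline follows from the protocol's expected reduction plus any spread in baseline. The sizes depend on baseline, response and placebo distributions that the documents do not give. Table 7 averages one dosing interval after the last simulated dose, not the trial's Week 36 window, so the arm spreads are indicative only.

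The primary percent-change conclusion is not at risk. For by-visit change, the absence of a covariate is inferred from the SAP's silence.

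The normality gap holds on the text alone.

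**What to change.** In SAP 3.4.2, analyse absolute change, time-averaged and by visit, by ANCOVA with treatment and the baseline of the analysed marker. Use HC3 robust standard errors, not ordinary ANCOVA ones. Keep the unadjusted ANOVA as a named sensitivity analysis. A treatment-by-baseline model may be added as a further sensitivity analysis if its variance includes the sampling variance of mean baseline. Group-specific variances for percent change are optional.

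In SAP section 6, record this change. There, either specify the normality check and the sensitivity analysis it triggers, or declare that process replaced by the robust-error analysis.

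The cost is a few lines of SAP text and code, with no new data. The drawbacks are a documented departure from the protocol's ANOVA and coverage against placebo that can fall to about 93% in the worst assumed scenario.
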